Two analyses, one within the trial, and another using a lifetime analysis based on the Sheffield Type 1 Diabetes Policy Model (currently in development through the NIHR Programme Grant), will be undertaken. For the within trial analysis (and hence those parameters that will subsequently be used in the Policy Model), missing data will be imputed with multiple imputation within STATA using ICE. An incremental cost effectiveness ratio (ICER) will be calculated with uncertainty around this characterised by plots on the cost-effectiveness plane and its associated cost-effectiveness acceptability curve and frontier. Deterministic sensitivity analysis will examine the effect of calculating QALYs using the SF-6D as based on the SF12 data. Sub-group analyses will be undertaken using the same populations as used within the clinical analysis, namely, for participants with HbA1c level below and ≥7.5% (58mmol/mol).

Site & Trial Closure Procedures

At the point at which all questionnaires and CRF's have been collected and entered (or participants have failed to respond despite reminders) and all data have been entered and cleaned, closure of the database will be approved. The end of the trial is defined by the point at which all questionnaires are returned and entered (not at last patient last visit) since the participants may return questionnaires after the visit. Questionnaire data will make up a significant proportion of the trial data.

Trial Pharmacovigilance

The safety of trial participants is of utmost importance and as such MHRA legislation and Sheffield CTRU SOPs will be followed in order to conduct the trial safely and to be able to assess any adverse events or serious adverse events that may occur during the trial. The following section outlines the methods for ensuring and assessing participant safety:

Definitions

The Medicines for Human Use (Clinical Trials) Regulations 2004 (SI 2004/1031) definitions:

Adverse Event (AE)- Any untoward medical occurrence in a subject to whom a medicinal product has been administered, including occurrences which are not necessarily caused by or related to that product.

Serious Adverse Event (SAE), Serious Adverse Reaction (SAR) or Suspected Unexpected Serious Adverse Reaction (SUSAR)-Any adverse event, adverse reaction or unexpected adverse reaction, respectively, that:

- Results in death
- Is life-threatening* (subject at immediate risk of death)

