Adverse events will be assessed for relationship to the study drug (Yes/No) and for seriousness (Yes/No). Events assessed as serious will also be reported as an SAE.

SAEs will be assessed for; seriousness, frequency, intensity, relationship to study product and relationship to pump. Expectedness of SAE's will be assessed against the reference safety information in the SmPC for the type of insulin used in the arm of the study the patient is randomised to.

The following criteria will be used when assessing SAEs: Intensity (severity):

- Mild - does not interfere with routine activities

- Moderate - interferes with routine activities

- Severe - impossible to perform routine activities

Relationship to the study product/pump:

- Unrelated - There is no evidence of any causal relationship. N.B. An alternative cause for the AE should be given.

- Unlikely - There is little evidence to suggest there is a causal relationship.

There is another reasonable explanation for the event (e.g. the participant's clinical condition, other concomitant treatment).

- Possible - There is some evidence to suggest a causal relationship. However, the influence of other factors may have contributed to the event

(e.g. the participant's clinical condition, other concomitant treatments).

- Probable - There is evidence to suggest a causal relationship and the influence of other factors is unlikely.

- Definite - There is clear evidence to suggest a causal relationship and other possible contributing factors can be ruled out.

- Not assessable - There is insufficient or contradictory information which cannot be supplemented or verified.

Reporting Procedures

All trial participants will be encouraged to contact and inform their local diabetes educator if they experience any of the medical problems outlined under SAEs or relevant AEs included (above). Any that are not picked up through general contact will be identified at follow up visits through educators enquiring about problems that the patients have had.

Relevant non serious ARs/AEs/UARs - Educators will record events on the adverse event paper CRF and database.

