Serious ARs/AEs/SUSARs - For any Serious Adverse Events an SAE paper CRF and database entry will be completed. The event will be assessed by the local Principal Investigator and the form faxed to the Sheffield Clinical Trials Research Unit (as delegated by the Sponsor) within 24 hours, except where exemptions from immediate reporting apply (see section below). In the absence of the PI, the form will be completed by the educator and faxed within 24 hours - when the PI becomes available a follow up form will be sent to the sponsor immediately. All SAE forms will be stored in the Site File.

Concomitant medications will only be recorded for SUSARs. In such cases

medications taken the 30 days prior to the event taking place will be reported.

[figure not shown]
A follow up SAE form with additional information will be sent if the event has not been completely resolved at the time of reporting.

The sponsor will notify the Chief Investigator and Sheffield CTRU of all SAEs. The sponsor (or delegate) will notify the MHRA and main REC of all SUSARs occurring during the study according to the following timelines; fatal and lifethreatening within 7 days of notification and nonlife threatening within 15 days. All investigators will be informed of all SUSARs occurring throughout the study.

Exemptions from Immediate Reporting

Episodes of Severe Hypoglycaemia and Diabetic Ketoacidosis are expected to occur in some patients with Type 1 Diabetes. Therefore any of these episodes, defined as SAEs, will be exempt from immediate reporting to the sponsor. Pregnancies will also be exempt from immediate reporting, as these will not be related to the trial treatment. In these instances the Principal Investigator will fax the SAE form to the Sheffield Clinical Trials Research Unit (as delegated by the Sponsor) within 4 weeks of the event being discovered.

Figure 6. Procedure for AE/SAE Reporting

threatening event.

Safety & Efficacy Parameters

Safety and efficacy parameters may be used in IMP trials to stop the trial if one of the treatments seems to be less safe or is working more effectively than the other. For example, if during this trial, there are more frequent hypoglycaemic or diabetic ketoacidosis episodes in the pump arm then the study may be stopped prematurely. The decision to stop the trial would be made by the Data Monitoring and Ethics Committee in agreement with the Sponsor (see trial supervision section below for further details).

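### The four-week reporting exemption for severe hypoglycaemia and DKA has no stated exception for fatal, life-threatening, pump-related or possible SUSAR cases

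*Protocol*

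**What the plan says.** All of the relevant text is in the Trial Pharmacovigilance part of protocol section 8.

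- **Reporting Procedures.** The local PI assesses each serious event and the form is faxed to the CTRU "within 24 hours, except where exemptions from immediate reporting apply (see section below").
- **Exemptions from Immediate Reporting.** The reason given is that "Episodes of Severe Hypoglycaemia and Diabetic Ketoacidosis are expected to occur in some patients with Type 1 Diabetes". The rule follows: "Therefore any of these episodes, defined as SAEs, will be exempt from immediate reporting to the sponsor". Pregnancies are added, on the separate ground that they will not be caused by trial treatment. For all three event types the form is due "within 4 weeks of the event being discovered".
- **Definitions.** The first seriousness criterion is "Results in death"; the second is immediate risk of death.
- **Assessment of Adverse Events.** Every SAE is rated for its relationship to the study product and, separately, to the pump. "Expectedness of SAE's will be assessed against the reference safety information in the SmPC for the type of insulin used" in the participant's arm.
- **Onward reporting of SUSARs.** The MHRA and main REC are told of "fatal and lifethreatening within 7 days of notification and nonlife threatening within 15 days".

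**The concern.** Exempting events that are common in the disease is an ordinary choice, and it suits routine admissions. Here, however, the exemption is defined by event type alone. Neither the outcome nor the cause of the episode changes the route, although the protocol collects both.

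The stated reason does not stretch that far. That some patients with type 1 diabetes will have DKA says nothing about a death from DKA, or about DKA after a pump failure. The protocol itself allows for the latter. Its section on DKA as an endpoint asks, for participants on a pump, whether there was a malfunction, and suspected malfunction is a listed adverse event. The Introduction describes ketoacidosis as potentially fatal. The argument used for pregnancy, that treatment cannot be the cause, is not offered for hypoglycaemia or DKA.

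If a participant died of DKA after a suspected pump failure, the site could comply with the protocol and still leave the sponsor uninformed for four weeks. Meanwhile other courses, of the 48 planned across 8 sites, could be starting participants on pumps.

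**Working it through.** No sample-size or power figure is involved. The check is a comparison of the rules and some date arithmetic.

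**Step 1. Does the exemption reach fatal and life-threatening cases?** It applies to any severe hypoglycaemia or DKA episode that is an SAE. Death and immediate risk of death are SAE criteria in the Definitions. The later classification paragraphs bring in both event types through hospitalisation, but a hospitalised episode can also be fatal or life-threatening, so that narrower route does not exclude such cases. They are covered.

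**Step 2. Does it reach treatment-related, pump-related or unexpected cases?** Relatedness and expectedness are assessed for SAEs, but the exemption does not refer to either. The 24-hour rule is headed as covering serious reactions, serious events and SUSARs together. The exemption from it has no SUSAR exception. These cases are covered on the wording.

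**Step 3. Permitted time from discovery to the CTRU.**
- Standard route: 24 hours = 1 day.
- Exempt route: 4 weeks × 7 = 28 days.
- Difference: 28 − 1 = 27 days.

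**Step 4. Permitted time from discovery to the MHRA and REC, if the case proves to be a SUSAR.** Maximum = time to the CTRU + onward limit. This takes both onward limits to run from notification of the CTRU as the sponsor's delegate.

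| Case | Standard route | Exempt route |
|---|---|---|
| Fatal or life-threatening | 1 + 7 = 8 days | 28 + 7 = 35 days |
| Other SUSAR | 1 + 15 = 16 days | 28 + 15 = 43 days |

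If the onward limits were instead read as running from discovery at the site, a form faxed on day 28 would already be 28 − 7 = 21 or 28 − 15 = 13 days past them. On either reading the two rules need to be reconciled.

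**Step 5. Is there another route by which the sponsor would learn sooner?** A database entry is required for every SAE and is not exempted, and section 11 places the database within the CTRU. No deadline or alert is attached to that entry, so it may shorten the delay but does not guarantee it.

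**The case against.** **Figure 6 is missing.** It sets out the AE/SAE reporting procedure, and only a fragment about a threatening event survives. It may contain the very exception that the text lacks, or it may only repeat the SUSAR timelines. This stands as a limit on confidence. An exception found only there would still have to be squared with the text's unqualified wording.

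**SUSARs may lie outside the exemption.** The Definitions list SAE, SAR and SUSAR as separate terms, and the exemption names only SAEs. That reading is available, so for SUSARs the fault may be an ambiguity. Nor is it shown that any such case would arise: the SmPC is not in the documents, so whether a severe hypoglycaemia or DKA could be unexpected against it is unknown.

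**Expectedness is not waived.** A reader might infer that the disease-level reasoning replaces the SmPC assessment. It does not. The form is still completed and the assessment still made; only the date by which the form must reach the CTRU changes.

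**The stopping provision is not undermined.** The protocol says that "if during this trial, there are more frequent hypoglycaemic or diabetic ketoacidosis episodes in the pump arm then the study may be stopped prematurely", and a reader might infer that the exemption blinds the DMEC to these events. But that example is a comparison of frequencies between arms. No passage gives the DMEC a 24-hour feed, and a lag of at most four weeks matters little to such a comparison.

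**The exempted events are not established as specific harms of the pump.** The protocol calls hypoglycaemia a side effect of insulin, which both arms receive, and reports that CSII reduced it in some studies. It does not say that DKA is a known harm of pumps. The point does not need either claim.

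**A remedy based on the pump alone would be poor.** It would leave unexpected insulin-related cases on the slow route and make reporting speed depend largely on arm. This stands, and it shapes the fix.

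**Conclusion.** The point holds on the running text. A severe hypoglycaemia or DKA SAE that is fatal, life-threatening, pump-related or potentially a SUSAR may reach the CTRU up to 28 days after discovery, 27 days later than the standard rule allows, with no site in breach.

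The totals of 35 and 43 days add two maximum limits and apply only if such a case turns out to be a SUSAR. They should not be read as a likely delay or as a demonstrated missed regulatory deadline. The conclusion assumes that Figure 6 contains no exception and that notification means receipt by the CTRU.

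The weight rests on prompt sponsor review of single grave or device-related events, in a trial whose question is the delivery device. Severity is moderate, because the gap is real and cheap to close but affects few events. Confidence is moderate because of the missing figure and the unsettled status of SUSARs.

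**What to change.** Add one sentence to the exemption. It should say that the exemption does not apply, in either arm, to a severe hypoglycaemia or DKA SAE that is:

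- fatal or life-threatening;
- judged at least possibly related to the pump, for example where malfunction is suspected; or
- suspected to be related to the study insulin and unexpected against the SmPC.

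These cases follow the 24-hour rule. Routine episodes keep the four-week route. Check Figure 6 and the SAE guidance for sites so that they agree with the text.

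The cost is a few more 24-hour faxes and a prompt causality judgement by the PI. Where the PI is absent, the existing provision for the educator to complete and fax the form, with follow-up by the PI, already serves. The same form and assessment are required now. The first and third limits apply equally to both arms; the second can by its nature arise only in participants using a pump, but it alters the speed of reporting and not whether an event is recorded.

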Hypoglycaemia is a major side effect of insulin treatment, which prevents many patients from achieving target glucose levels. CSII has been shown to reduce hypoglycaemia in some studies but since DAFNE and similar educational interventions are also associated with reduction in severe episodes we may have insufficient power to detect a difference in the rate of severe episodes between the two groups. During the last NICE appraisal of CSII, the question of the impact of moderate hypoglycaemia was raised. The point was made that moderate hypos, sufficient to interrupt activities of daily living, might because of greater frequency, have more cumulative effect on quality of life than severe hypos. Furthermore, moderate episodes are likely to be more frequent than severe events. We will therefore record both severe and moderate episodes of hypoglycaemia in participants. This should increase power and identify the ability of CSII to reduce rates of hypoglycaemia. It will also be possible to assess the effects of both, by comparing quality of life measures in those with only moderate hypos, versus those with moderate and severe.

Severe hypoglycaemia – any episode leading to cognitive impairment sufficient to cause either coma or requiring the assistance of another person to recover (27).

Moderate hypoglycaemia – any episodes which could be treated by that individual, but where hypoglycaemia caused significant interruption of current activity, such as having caused impaired performance or embarrassment or having been woken during nocturnal sleep.

Insulin dose

Some studies have indicated that CSII results in the use of less insulin. We will therefore record participants' self-reported insulin dose at each time point and calculate units/kg body weight.

Body Weight

If CSII treatment results in the use of less insulin, it may have a favourable effect on weight since with less insulin there is a propensity for the body to store fewer nutrients. We will therefore record weight at each time point of the trial.

Lipids and proteinuria

A recent study (26) reported little difference in HbA1c for CSII compared to MDI but found less progression to microalbuminuria in the CSII group, and also lower cholesterol and lower insulin dose.

Blood samples will be taken using local labs and lipids (including HDL cholesterol). Albumincreatinine ratio (a sensitive measure of proteinuria) will be measured from urine samples.

Diabetic-Ketoacidosis

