It is generally accepted that a difference of 0.5% in HbA1c is clinically worthwhile. To detect this difference with an SD of 1% at 80% power and 5% two sided significance using a t-test requires 64 patients per group for subjects \geq 7.5% (58mmol/mol) HbA1c. In order to allow for a clustering effect of the educators and a within-course intra-class correlation coefficient (ICC) of 0.05, which is common in diabetes care, the sample size increases to 84. Allowing also for a 10% drop out, the sample size per group becomes 93. Audit of the DAFNE database shows that 75% of subjects have an HbA1c of over 7.5% (58mmol/mol). With this in mind we require 124 subjects per group, i.e. 248 in total. We plan to recruit 280 subjects which increases the power to 85% but which allows for some variation in drop-out rates and the proportion of

patients with HbA1c ≥7.5% (58mmol/mol).

We believe that we should include patients who experience frequent hypoglycaemia but who might have existing levels of HbA1c that are near the target range since they may reduce hypoglycaemic episodes and can therefore still provide important information about quality of life. Yet, since there will be no change in HbA1c levels for these participants, including this data would reduce our statistical power to establish improvement in our primary endpoint. We will therefore stratify those entering the trial based on HbA1c levels of $\geq 7.5\%$ (58mmol/mol). The trial will be powered on the number of participants with an HbA1c $\geq 7.5\%$ (58mmol/mol), in whom a fall would reflect worthwhile improvements in glycaemic control but we will also calculate the number of participants in each group who achieve a HbA1c <7.5\% (58mmol/mol).

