The DAFNE database shows that 25% of subjects currently experience 'problems' recognising hypoglycaemia and 45% of them experience at least one severe hypoglycaemic episode over 2 years. To demonstrate the benefit of CSII over MDI with this number of patients, the percentage of patients who experience at least one severe hypoglycaemic episode would need to fall to about 25% over 2 years (a change from control of about 12% per year if the events were independent) for 80% power and 2 sided 5% significance level, allowing for 10% drop-out (using a chi-squared test with continuity correction and allowing for an ICC of 0.05). We would have power to demonstrate smaller differences in moderate hypoglycaemia although we are unable to provide precise estimates due to a lack of published data using our chosen definition.

Review of HbA1c baseline data

The sample size calculation is based upon 75% of subjects having an HbA1c \geq 7.5% (58mmol/mol). If the ratio of subjects with an HbA1c of \geq 7.5% to <7.5% is substantially lower than the expected 75:25 ratio, then the sample size (N=280) will not be sufficient to detect a difference in the primary outcome. Therefore, a review will be undertaken after Course 2, 4 and 5 to examine the proportions of recruited participants who are in each HbA1c category (i.e. \geq 7.5% or <7.5%). The trial statistician will look at the proportions in each category, and if the numbers of participants with an HbA1c \geq 7.5% threatens the ability of the trial to detect a difference in primary outcome (i.e. there are substantially more subjects recruited with an HbA1c <7.5% than anticipated), then an additional inclusion criteria will be added to limit recruitment only to participants with an HbA1c of \geq 7.5% in order to ensure the trial can detect a difference in the primary outcome.

Review of sample size in August 2012

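### The severe-hypoglycaemia power statement pairs a 45% event rate, worded as belonging to a quarter of subjects, with the whole-trial sample size

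*Protocol*

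**What the plan says.** Protocol section 9, Sample Size, takes two figures from the DAFNE database: "25% of subjects currently experience 'problems' recognising hypoglycaemia and 45% of them experience at least one severe hypoglycaemic episode over 2 years". It continues: "To demonstrate the benefit of CSII over MDI with this number of patients", the percentage of patients with at least one severe episode "would need to fall to about 25% over 2 years". The stated conditions are 80% power, two-sided 5% significance, 10% drop-out, a continuity-corrected chi-squared test and an ICC of 0.05. The number of patients meant is not spelled out; the text just before it plans 280 in total. No two-year rate is given for the remaining 75% of subjects or for all subjects together.

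Two other places bear on this. Under Hypoglycaemia in section 3, the protocol warns that "we may have insufficient power to detect a difference in the rate of severe episodes between the two groups". Section 9, Secondary Analysis, plans Poisson regression (zero-inflated if needed) on episode counts, with GEE for clustering, and expects this to be more powerful than the yes/no comparison.

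**The concern.** Read plainly, the word 'them' refers to the quarter of subjects who have trouble recognising hypoglycaemia. If it referred to all subjects, the 25% would play no part in the calculation. A rate that belongs to a high-risk quarter cannot serve as the control rate for the whole trial unless everyone else has the same rate. Nor can the whole-trial number be used for a comparison confined to that quarter.

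Hypoglycaemia stands beside glycaemic control in the aim given in the Trial Summary, and the Introduction says the trial is meant to inform NICE reviews. A reader who takes the 80% at face value would give a non-significant result on severe episodes more weight than the design supports.

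**Working it through.** **Inputs, all from the protocol**
- 140 per arm (Trial Summary).
- 10% drop-out, ICC 0.05, continuity-corrected chi-squared test, two-sided 5%, 80% power, 45% v 25% (section 9, Sample Size).
- 7 participants per course (section 9, Review of sample size in August 2012). The design effect is 1 + (7 - 1) x 0.05 = 1.30. The same factor gives the protocol's step from 64 to 84 for HbA1c (64 x 1.30 = 83.2).
- No inclusion criterion in section 5 selects for impaired recognition. The database share of 25% is therefore carried over: 0.25 x 280 = 70 participants, 35 per arm.

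**Step 1. Reproduce the stated figure.** The pooled-variance formula for two proportions is

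n = [1.96 x sqrt(2 x 0.35 x 0.65) + 0.84 x sqrt(0.45 x 0.55 + 0.25 x 0.75)]² / 0.20² = 88.1 per arm.

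The continuity correction gives n' = (n/4) x [1 + sqrt(1 + 4/(n x 0.20))]² = 97.8, so 98 per arm. Then 98 x 1.30 / 0.9 = 141.6 per arm, against 140 planned.

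In the other direction, 140 x 0.9 / 1.30 = 96.9 effective per arm. This gives 79.6% power for 45% v 25%, and a rate detectable at 80% power of 24.9%. The protocol's "about 25%" is therefore the result for all 280 participants, each with a 45% control rate.

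The annual gloss is consistent with this: 1 - sqrt(0.55) = 25.8%, 1 - sqrt(0.75) = 13.4%, difference 12.4%.

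**Step 2. The group the 45% describes.** After drop-out, 35 x 0.9 = 31.5 per arm. With 0.25 x 7 = 1.75 such participants per course, the design effect is 1 + 0.75 x 0.05 = 1.0375, giving 30.4 effective per arm.

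| Clustering assumption | Effective n per arm | Power, corrected | Power, uncorrected | CSII rate detectable at 80% (corrected) |
|---|---|---|---|---|
| None | 31.5 | 28% | 38% | 10.9% |
| 1.75 per course (1.0375) | 30.4 | 27% | 37% | 10.3% |
| Full design effect (1.30) | 24.2 | 21% | 30% | 6.7% |

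**Step 3. All participants.** The control rate is 0.25 x 45% + 0.75 x q = 11.25% + 0.75q, where q is the two-year rate in the other 75%. The protocol does not give q, so the values below are assumptions. The relative reduction is held at 25/45, with 96.9 effective per arm and the continuity correction.

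| q (assumed) | Control rate | CSII rate | Power |
|---|---|---|---|
| 0% | 11.25% | 6.25% | 16% |
| 10% | 18.75% | 10.4% | 30% |
| 20% | 26.25% | 14.6% | 45% |
| 30% | 33.75% | 18.75% | 60% |
| 35% | 37.5% | 20.8% | 67% |
| 45% | 45% | 25% | 80% |

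The stated power returns only in the last row, where subjects without recognition problems have the same rate as those with them.

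**The case against.** A reader might infer that the trial's real power for severe hypoglycaemia is 27%. The protocol does not support that. Its only planned subgroup split is by baseline HbA1c (section 9, Subgroup Analyses), so no comparison confined to participants with recognition problems is planned. The 27% describes the group to which the rate belongs; it is not the power of a planned analysis. It also assumes that the trial enrols exactly the database share. Section 9 wants patients with frequent hypoglycaemia included, while exclusion 14 removes those with a strong need for a pump, so the share could move either way.

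A reader might equally infer that all-participant power is at most 45%. That would need a ceiling of 20% on the unknown rate, and nothing in the protocol supplies one. Nor can the protocol exclude the possibility that 45% was meant for all subjects and the sentence is loosely worded. In that case the arithmetic is sound and the wording is the error.

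The consequences are also limited. The text states the fall that would be required, not one that is expected. Section 3 already warns of insufficient power for severe episodes. The planned analysis is of counts, not of the dichotomy. The 280 comes from HbA1c, and the sample-size reviews concern baseline HbA1c, drop-out and course size; none uses this sentence. Hypoglycaemia is one of six unranked biomedical secondary endpoints.

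All of this stands and lowers the severity. None of it makes the sentence correct as worded: the section 3 caution leaves the 80% claim in place, and no power figure is given for the Poisson analysis.

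**Conclusion.** The point holds, at moderate severity. As worded, the power statement joins a rate for about a quarter of subjects to the number of all participants, and 80% power for 45% v about 25% does not follow. In the population the rate describes, power is about 27% (21-28% with continuity correction, 30-38% without), and the fall needed for 80% is to about 10% (7-11%). In all participants, power depends on a rate the protocol does not report: 16% to 67% as that rate runs from 0% to 35%, and 80% only at 45%.

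These figures rest on the plain reading of 'them', 7 participants per course, a 25% share in the trial and, for the all-participant figures, an unchanged relative reduction. They apply to the dichotomous comparison that the protocol used for its statement, not to the planned count analysis. The primary endpoint and the planned 280 are unaffected.

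**What to change.** In section 9, Sample Size, state which population the 45% describes. Replace it with the two-year proportion of all DAFNE subjects who have at least one severe episode, taken from the same database, and recompute the difference detectable with 280 participants from that rate. If the 45% was in fact meant for all subjects, say so and delete or separate the 25% figure; the stated result can then remain. Add a cross-reference to the section 3 caution that severe hypoglycaemia may be underpowered.

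Do not put a power claim for participants with impaired recognition in its place, since no analysis of that group is planned. The cost is a change of wording and one database query. No further enrolment, design change or analysis change follows. Unless the 45% does apply to all subjects, the stated figure is likely to become less favourable.
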